### **Confidentiality Statement**

Philip Morris Products SA	Clinical Study Protocol	Confidential
P1-EXC-01-EU	Version 3.0 / 2 May 2019	Page 50 of 151

- 5. Subjects becomes an employee of the investigational site or any other parties involved in the study.
- 6. Lost to follow-up.
- 7. Violation of eligibility criteria after enrolment (i.e. if an eligibility criteria violation is retrospectively discovered after enrolment during the course of a study).

Subjects may be discontinued from the study for the following reasons:

1. Non-compliance with the study procedures based on the judgment of the Investigator.

For subjects who are discontinued, the reason for discontinuation should be documented in the source documents and in the CRF and subjects will undertake early termination procedures (Section 9.6).

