# 9.6 Early Termination Procedures

The following early termination procedures will be performed if a subject is discontinued from the study unless the subject refuses to perform the assessments:

- AE/SAE recording
- Device event recording
- Concomitant medications
- Clinical laboratory parameters (hematology, clinical chemistry, and urinalysis safety panel)

Data and information contained in this document are considered to constitute trade secrets and confidential commercial information, and the legal protections provided to such trade secrets and confidential information are hereby claimed under the provisions of applicable law. No part of this document may be publicly disclosed without the written consent of Philip Morris Products S.A

Philip Morris Products SA	Clinical Study Protocol	Confidential
P1-EXC-01-EU	Version 3.0 / 2 May 2019	Page 95 of 151

- Physical examination
- Spirometry
- Urine pregnancy test
- Vital signs
- ECG
- Information on the risk of smoking, smoking cessation advice, and debriefing on IQOS
- Return of *IQOS* device, mHealth wearable and product use diary.

Safety laboratory (hematology and clinical chemistry) may be done in non-fasting or fasting state. If subjects withdraw from the study or are discontinued during a planned visit, assessments required as per protocol for early termination that have been already performed during the planned visit should not be conducted again.

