6 SAMPLE SIZE JUSTIFICATION

The sample size of 20 per arm (smoking abstinence with training, IQOS with training, continued cigarette smoking with training) was determined based on previously published results, which reported a standard deviation of 14 mL/kg/min in VO₂max in the change

Confidentiality Statement

Philip Morris Products SA.	Statistical Analysis Plan	Confidential
P1-EXC-01-EU	Final 2.0	Page 30 of 71
Related to PMI-RRP-WKI-112487		SAD DI EYC OI EU

between groups which continued smoking and those who were smoking abstinent after participating in a 12-week training program (Albrecht, et al. 1998). This sample size allows a probability of 90% that the half-width of the 95% confidence intervals between two arms have a precision of approximately 10.3 mL/kg/min.

For example, if the mean difference in change between the cigarette arm and smoking abstinence arm was 12 mL/kg/min after training, we expect that if the experiment were repeated many times then on average 90% of the time the 95% confidence intervals of the mean differences between two arms will be within 1.7 and 22.3. To allow for a dropout rate of approximately 20%, the sample size will be 25 per arm. The IQOS-2 arm without training will mainly serve as a secondary analysis to the IQOS-1 arm with training, and the drop-out rate in this arm is expected to be lower. Therefore, only 15 subjects will be randomized to this arm.

CHANGES FROM THE PROTOCOL SPECIFIED STATISTICAL 7 ANALYSES

An exploratory analysis of VO2max and exercise capacity will be carried out on subjects with additional biochemical verification of smoking status.

8 **ANALYSIS SETS**

The main population for non-safety analysis will be the As Exposed Exercise Compliant Set. Safety will be analyzed using the Safety Set.

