8.3 As Exposed Exercise Compliant Set

The As Exposed Exercise Compliant Set (AEECS) consists of all randomized subjects who have at least one valid non-safety assessment after randomization, specifically we have

- post-randomization product (cigarette or IQOS) use experience if randomized to IQOS, • IQOS-2 or cigarette arm or
- no product use if randomized to the SA arm,

and who attended at least 34 of 38 (~90%) of the exercise training sessions except the subjects in IQOS-2 arm. Subjects in the IQOS-2 will be analyzed as exposed as they did not participate in the training. The AEECS will be analyzed by actual exposure (product use exposure, actual study arm).

Due to technical issues with the bike training equipment during the study, these rules are used to determine if a subject completed a training session for the purposes of defining the AEECS analysis set in addition to information regarding whether a training visit was done or not. We define a training session to be completed if a minimum of 20 or more minutes of exercise was done. If the training time is unknown then the session is considered to be not done. These checks from the protocol deviation dataset will be done regardless of whether data from the exercise training is available or not.

For a training session to be considered as not done from the protocol deviations (PD) dataset, the PD description will be checked for the following,

- "Bike training was not done" •
- "Bike training was partially completed for less than 20 min ..."
- "Bike training was partially completed for unknown number of minutes ..."

A bike training session is considered as complete if the following description for bike training is provided in the PD dataset,

- "Bike training was completed..."
- "Bike training was partially completed for at least 20 min..." •

In the case where there are inconsistencies between the PD dataset and bike training data, ie, for example bike training was marked as complete but the PD descriptions says otherwise, the PD rules will be used to determine completion of a bike training session.

Confidentiality Statement

Philip Morris Products SA.	Statistical Analysis Plan	Confidential
P1-EXC-01-EU	Final 2.0	Page 32 of 71
Related to PMI-RRP-WKI-112487		

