9.6.1 Endpoint Analyses

The following non-safety endpoints will be analyzed using the AEECS considering the actual study arm (i.e. product use exposure). The following sections describe the statistical models used in analyzing the endpoints as well as descriptive statistics used for summarizing the data.

In general, for model based analysis all visit data will be used and analyzed within the same model.

- 9.6.1.1 Statistical Analysis of Endpoints
- 9.6.1.1.1 To evaluate changes in VO₂max in subjects switching to IQOS (with and without training), continuing to smoke cigarettes (with training) and being smoking abstinent

A linear mixed effects model will be used to estimate the difference in VO₂max between each arm (SA arm, IQOS-1+IQOS-2 combined arm, Dual-1+Dual-2 arm) versus cigarette arm one week after randomization (V4) and after completion (SA arm, IQOS-1 arm, IQOS-2 arm, Dual-1 arm) of the 12-week training program (V43). The degrees of freedom will be adjusted by using Kenward Roger (KR) method and the Saitterthwaite method will be used in case of convergence issues. Both V4 and V43 data will be used together in the same model. At V4, both IQOS-1 and IQOS-2 will be combined into a single IQOS group as these subjects did not attend any exercise training.

The dependent variable will be the VO₂max change from baseline with baseline VO₂max, arm, visit, sex, age and visit*arm as *fixed* covariates and subject fitted as a random effect. In addition, the following *exploratory* covariates BMI, RPC, COHb levels at each visit, cigarette consumption at V1, IPAQ score at V1, average step count 2 weeks prior to visit, self-reported daily cigarette consumption (from randomization until each visit), cigarette smoking 30-60 minutes before test for subjects in cigarette arm and IQOS use 30-60 minutes before test for subjects in IQOS arm will be assessed for adequacy in the model using a step-wise (backward) approach through the following algorithm.

Data and information contained in this document are considered to constitute trade secrets and confidential commercial information, and the legal protections provided to such trade secrets and confidential information are hereby claimed under the provisions of applicable law. No part of this document may be publicly disclosed without the written consent of Philip Morris Products S.A

Philip Morris Products SA.	Statistical Analysis Plan	Confidential
P1-EXC-01-EU	Final 2.0	Page 40 of 71
Related to PMI-RRP-WKI-112487		

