9.6.1.3 Supportive/Sensitivity Analyses

If deemed appropriate, selected endpoint analyses will additionally be performed for the FAS.

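### The 34-of-38-session rule selects IQOS-1 but not IQOS-2, so their V43 contrast can mix selection with the effect of near-full training

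*SAP*

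**What the plan says.** SAP section 8 states: "The main population for non-safety analysis will be the As Exposed Exercise Compliant Set". SAP 8.3 defines that set (AEECS) by a valid post-randomisation assessment, the product use expected of the arm, and an attendance condition: "and who attended at least 34 of 38 (~90%) of the exercise training sessions except the subjects in IQOS-2 arm". On what counts as a session it adds: "We define a training session to be completed if a minimum of 20 or more minutes of exercise was done". Sessions last 40 minutes (Protocol 7.6.3). IQOS-2 has 12 weekly visits of its own, but no minimum number is set for them.

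SAP 6 gives the purpose of the untrained arm: "The IQOS-2 arm without training will mainly serve as a secondary analysis to the IQOS-1 arm with training". SAP Table 5 lists IQOS-2 as a comparator for IQOS-1 at V43. That layout is used for VO2max, exercise capacity, blood composition and respiratory parameters, for health markers at V14, V28 and V43, and for monthly step counts. Body fat and waist follow a similar layout, and weight is compared between groups at V14, V28 and V43 (SAP 9.6.1.1.1 to 9.6.1.1.7).

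The Full Analysis Set (FAS, SAP 8.1) has no attendance rule and is analysed by randomised arm. Its role is conditional (SAP 9.6.1.3): "If deemed appropriate, selected endpoint analyses will additionally be performed for the FAS". The table list in SAP 13.2 does contain FAS model tables for VO2max (15.2.2.1.6 to 15.2.2.1.9) and exercise capacity (15.2.2.2.6 to 15.2.2.2.9), without the topline flag that the AEECS versions carry. It lists no FAS model tables for steps, health markers, weight, body fat, waist, blood composition or respiratory parameters.

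**The concern.** IQOS-2 is there to show what switching does without training, so IQOS-1 versus IQOS-2 is the comparison from which a reader will take the added effect of training. In the main set, subjects who could not or would not keep up a 12-week programme are taken out of one side only. If those who persist would in any case have improved more, that difference is read as a training effect, and randomisation does not protect against it.

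The rule also reaches back in time. Whether a subject meets it is settled only towards the end of training. An IQOS-1 subject who stops in week 5 therefore loses their V14 health markers and Month 1 steps from the main set, whereas an IQOS-2 subject who leaves at the same point keeps theirs, because SAP 9.1.4 analyses dropouts on the data available. The link between persistence and outcome is easiest to imagine for steps and weight, and these are among the endpoints with no by-arm FAS table.

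**Working it through.** **The plan's own figure.** Inputs from SAP 6: SD 14, 20 per arm, 95% interval, 90% probability. Half-width = t(0.975, 38) × 14 × √(χ²(0.90, 38)/38) × √(2/20) = 10.23, against the stated 10.3 or so. Inflation for dropout: 20/(1 − 0.20) = 25 per arm. Both reproduce. The cut-off 34/38 is 89.5%.

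**Precision of the contrast at issue.** The expected half-width is t × 14 × √(1/n₁ + 1/n₂):

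- 20 versus 15: 9.7 mL/kg/min, or 0.695 SD.
- 25 versus 15: 9.3 mL/kg/min.

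**Illustrative selection shift.** Suppose a normally distributed tendency to attend has correlation r with the change the subject would have shown anyway, and the lowest fraction q of IQOS-1 is removed. The mean of those kept then moves by SD × r × φ(z_q)/(1 − q). The last factor is 0.350, 0.497 and 0.644 for q = 0.20, 0.30 and 0.40. The documents give neither q nor r; both are assumptions. At SD 14, in mL/kg/min:

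| q removed | r = 0 | r = 0.2 | r = 0.3 | r = 0.5 |
|---|---|---|---|---|
| 0.20 | 0 | 0.98 | 1.47 | 2.45 |
| 0.30 | 0 | 1.39 | 2.09 | 3.48 |
| 0.40 | 0 | 1.80 | 2.70 | 4.51 |

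At q = 0.20 and r from 0.2 to 0.5 the shift is 0.070 to 0.175 SD, which is 10% to 25% of the 0.695 SD half-width whatever the SD. At an assumed SD of 5 it is 0.35 to 0.87 mL/kg/min.

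**Effect on the interval.** In a simulation with 25 and 15 randomised and no true difference, the nominal 95% interval excluded zero in 6% to 8% of trials at q = 0.20 and in 8% to 14% at q = 0.40, for r of 0.3 to 0.5. With r = 0 the figure was about 5%.

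**What q means at V43.** A subject who leaves before V43 has no V43 value in either set, since SAP 9.1.4 imputes nothing. At V43 the two sets therefore differ on attendance only through IQOS-1 subjects who reach the visit with fewer than 34 sessions. At V14, V28 and in the monthly summaries, later dropouts from IQOS-1 are removed as well.

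**The case against.** Several points on the other side stand.

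- **Dose, not only selection.** In IQOS-1, attendance is the amount of training received. Part of any correlation between attendance and change is the training effect itself, so the gap between AEECS and FAS is partly a legitimate change of question. Only the remaining part of r is selection, and its sign is not known.
- **Adjustment.** The VO2max model includes baseline VO2max, sex and age and tests further covariates. The models for other endpoints also adjust for subject characteristics. Any prior advantage in fitness is partly handled, and the illustration takes no credit for this.
- **IQOS-2 is not wholly unfiltered.** It must have product use and a valid assessment, it passes through the same diary classification, and it will have some dropout. SAP 8.5.1 counts a missed scheduled visit as a major deviation that may lead to exclusion. None of this sets an attendance threshold to match 34 of 38.
- **A check is partly foreseen.** FAS tables exist for the two lead endpoints, and the study tests no hypothesis (SAP 3.3.1). What is at risk is the estimate and its interval, not a formal error rate.

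Three stronger readings are tempting, but the documents do not support them. First, a reader might take the plan's 20% as the share removed by the session rule; SAP 6 gives it as a dropout allowance. Second, a reader might express the shift as a share of the 12 mL/kg/min in SAP 6; that figure is an example for cigarettes versus abstinence, and no IQOS-1 versus IQOS-2 difference is assumed anywhere. Third, Protocol 5.2 lets a subject be discontinued for "Non-compliance with the study procedures based on the judgment of the Investigator", and the early-termination list in Protocol 9.6 has no VO2max or exercise capacity test. A reader might infer that poor attenders will be taken out before V43. The first provision is permissive, and no passage makes missed sessions a trigger.

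**Conclusion.** The asymmetry is plain in SAP 8.3: the main IQOS-1 versus IQOS-2 contrast at V43, and those at earlier visits and by month, condition one arm on attendance after randomisation. They can therefore include selection as well as the effect of near-full training. That they do include it is not shown. With 20% removed, SD 14 and an assumed selection correlation of 0.2 to 0.5, the shift would be about 1.0 to 2.5 mL/kg/min before covariate adjustment, well below the half-width of about 9.7. It is zero if attendance carries no information about outcome beyond the training itself. This does not undermine the study. It is a gap in reporting that can be closed cheaply, and it matters most for the endpoints that have no FAS table.

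**What to change.** 1. In SAP 9.6.1.3, delete the opening condition. State that IQOS-1 versus IQOS-2 at V43 in the FAS, by randomised arm, will be reported beside the AEECS contrast, using Tables 15.2.2.1.7 and 15.2.2.2.7 for VO2max and exercise capacity.
2. Add FAS model tables for steps, health markers, weight, body fat, waist, blood composition and respiratory parameters.
3. Report how many IQOS-1 subjects the 34-session rule removes, and their baseline profile beside those kept.

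The cost is SAP wording and a few reruns of existing code. The FAS estimate dilutes the effect of full training and includes dual users, so it changes product-use grouping as well as attendance. For that reason the AEECS should stay as the near-full-training estimate rather than be replaced. The FAS does not recover V43 values that were never measured. No change to the discontinuation provisions of Protocol 5.2 is proposed.

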# **12.2** Determination of Sample Size and Power Consideration

The sample size of 20 per arm (smoking abstinence with training, *IQOS* with training, continued cigarette smoking with training) was determined based on previously published results, which reported a standard deviation of 14 mL/kg/min in VO2max in the change between groups which continued smoking and those who were smoking abstinent after participating in a 12-week training program (2). This sample size allows a probability of 90% that the half-width of the 95% confidence intervals between two arms have a precision of approximately 10.3 mL/kg/min. For example, if the mean difference in change between the cigarette arm and smoking abstinence arm was 12 mL/kg/min after training, we expect that if the experiment were repeated many times then on average 90% of the time the 95% confidence intervals of the mean differences between two arms will be within 1.7 and 22.3. To allow for a dropout rate of approximately 20%, the sample size will be 25 per arm. The *IQOS*-2 arm without training will mainly serve as a secondary analysis to the *IQOS*-1 arm with training, and the drop-out rate in this arm is expected to be lower. Therefore, only 15 subjects will be randomized to this arm.

Data and information contained in this document are considered to constitute trade secrets and confidential commercial information, and the legal protections provided to such trade secrets and confidential information are hereby claimed under the provisions of applicable law. No part of this document may be publicly disclosed without the written consent of Philip Morris Products S.A

Philip Morris Products SA	Clinical Study Protocol	Confidential
P1-EXC-01-EU	Version 3.0 / 2 May 2019	Page 103 of 151

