Missing data for self-reported daily use will not be imputed and we will assume that the derived average monthly use from non-missing data is representative of the actual usage. For each analysis period (Week 1 or Overall), if more than 50% of product use data is not available then the subject will be grouped into the 'Others' product use arm. Therefore, it is possible that a subject is not considered for statistical modelling as it is grouped into 'Others' for Week 1 (3 out of 7 days of product use data only) but available for analysis for the entire study period if more than 50% of product use data was eventually collected throughout the study. A subject may have switched product use groups throughout the study and the total number of subjects in an arm may fluctuate over time depending on the actual product use.

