9.1.1 Stratified Presentation

Stratification criteria for the evaluation are:

- Randomized study arm Cigarette, IQOS-1, smoking abstinence (SA), IQOS-2) randomized arm.
- Product use (actual arm) i.e. actual product use exposure categorized based on self-reporting and biochemical verification according to Section 5.5.1 "Product Use Pattern":

Confidentiality Statement

Data and information contained in this document are considered to constitute trade secrets and confidential commercial information, and the legal protections provided to such trade secrets and confidential information are hereby claimed under the provisions of applicable law. No part of this document may be publicly disclosed without the written consent of Philip Morris Products S.A

Philip Morris Products SA.	Statistical Analysis Plan	Confidential
P1-EXC-01-EU	Final 2.0	Page 34 of 71
Related to PMI-RRP-WKI-112487		SAP_P1-EXC-01-EU

- o Cigarette,
- o IQOS-1,
- Smoking Abstinence (SA),
- IQOS-2,
- Dual users considered for IQOS-1 (Dual-1),
- Dual users considered for IQOS-2 (Dual-2),
- Cigarette consumption at V1 (10 to 19 cigarettes, more than 19 cigarettes per day)
- Sex (male, female)
- Age (<50, ≥ 50 years i.e. $21 \le Age < 50$ and $50 \le Age \le 65$])

The main stratification criterion for the evaluation is the actual product exposure, whereas data will be listed by randomization arm.

Further stratification by cigarette consumption and sex will be done for the analysis of VO_2max and exercise capacity and where explicitly defined. Further stratification by age and BMI will be done only where explicitly defined (e.g. for demographic data).

The AEECS, AEBECS and the Safety Set will be analyzed by actual study arm (product use exposure). The FAS will be analyzed by randomized study arm.

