9.4 Measurement of Product Compliance

There is no restriction on allocated product use.

Although subjects are being requested to use solely the product allocated to their respective study arm, it is considered that not all subjects randomized to the IQOS arms or to the cigarette arm will exclusively use the randomized product at all times during the study. Subjects may concomitantly use IQOS and cigarettes (dual use). To account for dual use of IQOS and cigarettes, adjustments for cigarette or IQOS use outside of the intended arms will be done statistically. Similarly, it is expected that subjects in the SA arm who should stay abstinent during the study may relapse to the use of tobacco or nicotine-containing tobacco products (e.g., cigarette or IQOS). In addition to the randomized arms of IQOS, Cigarette or SA , additional arms comprising of the categories Dual-1 and Dual-2 according to the definition in Section 9.1.1 "Stratified Presentation" will be used in part of the analysis. Subjects in the 'Others' product use group (Figure 2) will only be listed and not analyzed.

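### Unless Figure 2 excludes them, untrained IQOS-2 subjects classed as cigarette users (or, more narrowly, as abstinent) join the trained Cigarette and SA groups at V43 and tilt the IQOS-1 contrasts towards IQOS-1

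*SAP*

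**What the plan says.** Objective 1 (Protocol 3.1, SAP 3.1) describes both the smoking and the abstinent comparators as trained. SAP 8 makes the AEECS the main non-safety set. Under SAP 8.3, subjects in the three training arms need 34 of 38 sessions to enter it. IQOS-2 subjects do not, and of them the section says: "Subjects in the IQOS-2 will be analyzed as exposed as they did not participate in the training". An IQOS-2 subject does need some cigarette or IQOS use after randomisation to enter.

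SAP 9.1.1 lists the actual-use groups: Cigarette, IQOS-1, SA, IQOS-2 and two dual-use groups, the second being "Dual users considered for IQOS-2 (Dual-2". IQOS and dual use are therefore split by training; Cigarette and SA are not.

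The plan expects movement between groups. SAP 9.4 anticipates that "not all subjects randomized to the IQOS arms or to the cigarette arm will exclusively use the randomized product at all times", and SAP 5.5.1 says: "A subject may have switched product use groups throughout the study". Protocol 5.2 does not discontinue a subject for using another product, so a relapsed IQOS-2 subject can reach V43. The group used for the training effect comes from average consumption between V3 and V43, classified by Figure 2.

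SAP Table 5 uses Cigarette as the V43 reference for IQOS-1, SA and Dual-1, and compares IQOS-1 with SA. The models in SAP 9.6.1.1.1 and 9.6.1.1.2 have no training term, fixed or exploratory.

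**The concern.** The V43 contrasts are meant to show whether product use changes the response to 12 weeks of training. That reading requires everyone in the reference group to have been assigned to train. The text separates trained from untrained subjects for two kinds of user and leaves the other two kinds undivided. If an IQOS-2 subject is classed by use alone, a returned smoker falls into Cigarette without having trained. The group's mean change at V43 then drops for a reason unrelated to the product, and IQOS-1 looks better beside it. The direction agrees with the study's premise that smoking blunts trainability, so a reader could not tell the artefact from the effect.

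VO2max and exercise capacity are the main endpoints exposed. Table 5 is also used for blood composition, monthly step count and biological health markers, and for body fat and waist circumference in similar form. V4 is not affected, because nobody has trained by then.

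**Working it through.** **1. The plan's own figure.** Inputs from SAP 6 and Protocol 12.2: "The sample size of 20 per arm", a source "which reported a standard deviation of 14 mL/kg/min", a "precision of approximately 10.3 mL/kg/min", and "To allow for a dropout rate of approximately 20%, the sample size will be 25 per arm".

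- Half-width reached with 90% assurance: t(0.975; 38) × 14 × √(2/20) × √(χ²(0.90; 38)/38) = 8.96 × √(χ²(0.90; 38)/38) = 10.23. Conditional on the interval covering the true difference it is 10.25. Both agree with the stated 10.3.
- 12 ± 10.3 = 1.7 to 22.3; 20/(1 − 0.2) = 25; 90 × 5/18 = 25 and 90 × 3/18 = 15.

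These figures reproduce. They are used below only for n = 20, for the limit of 15 IQOS-2 subjects, and as a yardstick.

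**2. Where the text places an IQOS-2 subject at V43** (SAP 5.5.1, 8.3, 9.1.1, 9.4).

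| Use after randomisation | In AEECS? | Group the text offers | Result |
|---|---|---|---|
| Classed as IQOS | Yes | IQOS-2 | Kept apart |
| Classed as dual | Yes | Dual-2 | Kept apart |
| Classed as cigarettes | Yes | Cigarette only | Pooled with trained subjects |
| Some use, then essentially none | Yes | SA only | Pooled with trained subjects |
| No product at all | No | None | Not analysed |
| More than half of diary data missing | Yes | Others | Not modelled |

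Rows three and four are the gap. Missing diary data is the only trigger for Others that is put into words, and it does not describe a subject with a complete cigarette diary. Figure 2 may contain further triggers.

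**3. Size of the dilution.** Let G be the difference in mean V43 change between trained and untrained subjects with the same product use. If n trained subjects have mean change μ + G and k untrained ones have μ, the pooled mean is μ + G × n/(n+k). The group loses G × k/(n+k), and IQOS-1 minus that group rises by the same amount. For time to complete the exercise test, where a gain is a shorter time, the sign reverses but the favoured arm does not.

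The documents give neither k nor G. The table assumes G = 2, 4 or 6 mL/kg/min.

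| k | Loss at n = 20 | Loss at n = 25 | Shift at n = 20 for G = 2 / 4 / 6 (mL/kg/min) |
|---|---|---|---|
| 1 | 1/21 = 4.8% of G | 3.8% | 0.10 / 0.19 / 0.29 |
| 3 | 3/23 = 13.0% | 10.7% | 0.26 / 0.52 / 0.78 |
| 5 | 5/25 = 20.0% | 16.7% | 0.40 / 0.80 / 1.20 |
| 15 (limit) | 15/35 = 42.9% | 37.5% | 0.86 / 1.71 / 2.57 |

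A simulation of 20,000 trials with G = 4 and a within-group SD of 4 (both assumed) gave shifts of 0.21, 0.52 and 0.79 for k = 1, 3 and 5, against 0.19, 0.52 and 0.80 by formula. These are simple means; the fitted model adjusts for covariates, but none of them identifies training.

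**4. SA versus Cigarette.** With subscripts S and C for the two groups, this contrast shifts by G_C × k_C/(n_C + k_C) − G_S × k_S/(n_S + k_S). It can move either way, or not at all.

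**The case against.** The strongest reply is that Figure 2 governs the routing and its content is not in the text supplied, which is no fault of the plan. The list in SAP 9.1.1 is not exhaustive: SAP 9.4 attributes an Others group to Figure 2 and keeps it out of the analysis. The lack of an untrained Cigarette group therefore does not prove that these subjects land in Cigarette. This stands, and it makes the point conditional.

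Second, the authors plainly considered training. They pool IQOS-1 with IQOS-2 only at V4, compare IQOS-2 only with IQOS-1 and Dual-2 at V43, and in SAP 9.6.1.1.3 leave out only IQOS-2 and Dual-2 as untrained. The sentence quoted from SAP 8.3 could simply explain the attendance exemption. This shows that Cigarette and SA were assumed to be trained groups; it is not a rule that makes them so.

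Third, an unaffected analysis exists. The FAS is analysed by randomised arm, and SAP 13.2 lists V43 FAS tables for VO2max (15.2.2.1.7) and exercise capacity (15.2.2.2.7). That helps, but SAP 9.6.1.3 makes FAS analyses discretionary. The AEBECS is no remedy: it is a subset of the AEECS, and SAP 8.4 adds no criterion for cigarette users.

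Fourth, the effect may be small. Partial relapse may be classed as Dual-2, and at k = 3 the assumed shift of 0.26–0.78 is 2.5–7.6% of the planned half-width of 10.3. True, and no hypothesis is tested; but the shift is systematic and better precision would not remove it.

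A reader might also infer that an IQOS-2 subject who uses nothing enters SA. SAP 8.3 rules that out, because some product use is needed for entry. Only someone who used a product and then essentially stopped could arrive there, so the SA route is narrow.

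**Conclusion.** The point holds conditionally. As written, SAP 8.3 and 9.1.1 allow untrained IQOS-2 subjects to be counted with trained Cigarette subjects at V43 and, by a narrower route, with trained SA subjects. If that happens and G is positive, IQOS-1 versus the affected group shifts towards IQOS-1 by G × k/(n+k), or 4.8% to 20.0% of G for k = 1 to 5 at n = 20. The sizes in mL/kg/min rest on assumed values of k and G.

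Two stronger readings are tempting. One is that the contamination is built into the plan; the documents do not show this, because Figure 2 could send these subjects to Others. The other is that SA versus Cigarette must be exaggerated; it need not be, because dilution of both groups can offset. Severity: should-fix, conditional on Figure 2.

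**What to change.** In SAP 8.3 and 9.1.1, state in words that for every endpoint after V4 the Cigarette and SA actual-use groups contain only subjects randomised to a training arm. IQOS-2-randomised subjects classed as cigarette or abstinent should be listed or summarised separately, for example as Cigarette-2 and SA-2, and left out of the Table 5 contrasts. At V4 they may stay in the pooled groups. It would also help to make the V43 FAS analyses by randomised arm firm rather than discretionary.

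The cost is a few lines of text and one condition in the actual-arm derivation. A few subjects may leave the V43 reference groups, with a small loss of precision. If Figure 2 already excludes them, only the wording changes. Either way, this dilution becomes zero and the comparators match Objective 1.
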